**LIST OF ABBREVIATIONS (EXAMPLES)**

AE	Adverse Event
ALT	Alanine Aminotransferase
ALC	Absolute Lymphocyte Count
ASCO	American Society of Clinical Oncology
AST	Aspartate Aminotransferase
BUN	Blood Urea Nitrogen
CBC	Complete Blood Count
CMP	Comprehensive Metabolic Panel
CR	Complete Response
CT	Computed Tomography
CTCAE	Common Terminology Criteria for Adverse Events
DLT	Dose Limiting Toxicity
DOT	Disease Oriented Team
DSMB	Data and Safety Monitoring Board
ECOG	Eastern Cooperative Oncology Group
FDA	Food and Drug Administration
GCP	Good Clinical Practice
H&P	History & Physical Exam
HRPP	Human Research Protections Program
IDE	Investigational Device Exemption
IHC	Immunohistochemistry
IND	Investigational New Drug
IV (or iv)	Intravenously
MRI	Magnetic Resonance Imaging
MTD	Maximum Tolerated Dose
NCI	National Cancer Institute
ORR	Overall Response Rate
OS	Overall Survival
PBMCs	Peripheral Blood Mononuclear Cells
pCR	Pathologic Complete Response
PD	Progressive Disease
PET	Positron Emission Tomography
PFS	Progression Free Survival
p.o.	peros/by mouth/orally
PR	Partial Response
RCB	Residual Cancer Burden
RECIST	Response Evaluation Criteria in Solid Tumors
SAE	Serious Adverse Event
SCCC	Simmons Comprehensive Cancer Center
SD	Stable Disease

---

SGOT	Serum Glutamic Oxaloacetic Transaminase
SPGT	Serum Glutamic Pyruvic Transaminase
WBC	White Blood Cells

**STUDY SCHEMA**

## STUDY SUMMARY

Title	The Role of  Ga PSMA-11 in Enhancing Diagnosis of Primary and Metastatic Prostate Cancer
Short Title	 Ga PSMA-11 PET/CT in Prostate Cancer
Protocol Number	STU-2019-1198
Phase	Phase 2
Methodology	Unblinded single arm imaging study
Study Duration	2 years
Study Center(s)	Single-center
Objectives	To assess the ability of 68Ga PSMA-11 PET/CT to increase diagnostic accuracy in localizing primary and metastatic lesions in patients with suspected prostate cancer and elevated PI-RADS scores and PSA.
Number of Subjects	20
Diagnosis and Main Inclusion Criteria	Patients with suspected prostate cancer who have at least one PI-RADS 5 lesion, or at least one PI-RADS 4 lesion and PSA $\geq 10$ ng/mL on standard conventional imaging multiparametric MRI (mp-MRI) of the prostate and scheduled for biopsy or radical prostatectomy.
Study Product(s), Dose, Route, Regimen	 Ga Prostate Specific Membrane Antigen-11, single intravenous injection, 1.8 – 2.2 MBq/kg body weight
Duration of administration	Single intravenous administration
Reference therapy	Imaging study only
Statistical Methodology	Descriptive statistics only

## 1.0 BACKGROUND AND RATIONALE

### 1.1 Disease Background

In developed countries, prostate cancer is the most common malignancy in men and the third leading cause of death in men [1, 2]. Despite being a common cancer, it has proven challenging to diagnose accurately both primary and metastatic lesions. There are numerous reasons for this challenge including the insensitivity of serum prostate specific antigen(PSA) in distinguishing benign from malignant disease, sampling errors in unguided biopsies of the prostate, and the multifocal nature of prostate cancer lesions within the prostate [3].

In the evaluation of primary prostate cancer, the use of multi parametric MRI (mp-MRI) has increased the detection of primary prostate cancer, but there is still a significant number of undetected lesions using this technique. A recent large study [3], which correlated pre-prostatectomy mp-MRI imaging with post prostatectomy whole mount pathology (WMP) of the resected gland, reported that less than half of all individual prostate cancer lesions were identified. These tumors were most commonly small lesions (<1 cm), multifocal lesions, lesions associated with Gleason score < 3+3, and with Prostate Imaging –Reporting and Data System (PI-RADS) v2.1 score < 4. However, some of these undetected lesions have elevated PSA and Gleason scores  $\geq 7$ , making more aggressive biologic behavior likely [3].

In addition, accurate localization of metastatic lesions outside the prostate with standard of care imaging, such as magnetic resonance imaging (MRI) and computed tomography (CT) of the pelvis, lack sensitivity as they are dependent upon size criteria and may not detect disease in smaller nodes [4]. Planar bone scintigraphy, standard of care in high-grade tumors, may also under identify small lesions and may lack specificity due to uptake in additional common benign disease [5]. For these reasons, it is desirable to pursue additional imaging with greater sensitivity and specificity for detecting primary tumors as well as staging for metastatic disease [6].

### 1.2 Study Agent(s)/Therapy(ies) Background and Associated Known Toxicities

In the last several years, molecular imaging using a variety of radiopharmaceuticals has been used to enhance the detection of both primary and metastatic lesions, with varying degrees of sensitivity. Some of the most promising of these are radio-ligands that target prostate specific membrane antigen (PSMA), a glycoprotein membrane antigen that is over expressed in the majority of prostate cancers. One of these ligands is  $^{68}\text{Ga}$  labelled (Glu-NH-CO-NH-Lys(AHX)-HBED-CC;HBED=N,N'-bis[2-hydroxy-5-(carboxyethyl)benzyl]ethylenediamine-N,N'-diacetic acid) ( $^{68}\text{Ga}$  PSMA-11) which can be imaged using positron emission tomography with computed tomography (PET/CT) [1].  $^{68}\text{Ga}$  PSMA-11 PET/CT has been used extensively to evaluate patients with prostate cancer outside of the United States. It has been found useful in the diagnosis of primary tumors [5, 7] and metastatic lesions [1, 8-10]. It has been useful in the setting of biochemical relapse, when PSA begin to rise, but is still relatively low, following definitive therapy [11, 12]. According to clinicaltrials.gov, there are currently (June 2019) 68 ongoing trials using  $^{68}\text{Ga}$  PSMA-11 in the United States and other countries.

The toxicity of the precursor PSMA-11 has been reported to be below the no-observed-adverse-effect-level (NOEL). 86  $\mu\text{g}$  PSMA-11 per kg body weight administered i.v. in one species (female and male rat) in the single-dose acute toxicity was below the NOEL.

Based on the referenced study, a safety factor of 1000 can be assumed for a maximum human dose of PSMA-11 of 6.3 nmol or 6  $\mu\text{g}$  per injection for a standardized patient of 70 kg body weight at a maximal concentration of 0.6  $\mu\text{g}/\text{mL}$  (AURIGON [contact]) [15].

---

**1.3 Other Agents**

None.

**1.4 Rationale**

A recent case report has documented that  $^{68}\text{Ga}$  PSMA-11 PET/CT may identify a prostate primary lesion even when mp-MRI does not [13]. In addition, mp- MRI may detect only a single lesion with PI-RADS v 2.1  $\geq 4$  but prostate cancer is often multifocal [3] and with the addition of  $^{68}\text{Ga}$  PSMA-11 PET/CT, those additional prostatic lesions might be identified. Several studies have demonstrated that early dynamic PET/CT imaging immediately after injection of  $^{68}\text{Ga}$  PMSA-11 can enhance primary prostate cancer detection as tumor uptake begins rapidly after injection and before the urinary bladder begins to fill with excreted tracer [7, 14].

In addition to identifying primary prostatic lesions, it is possible that  $^{68}\text{Ga}$  PMSA-11 PET/CT may be able to detect more metastatic disease than that detected on current standard of care staging imaging for patients with elevated PI-RADS scores and PSA values.  $^{68}\text{Ga}$  PMSA-11 PET/CT is reported to be able to detect small suspicious nodes and extra prostatic lesions due to its greater sensitivity and specificity compared to a variety of other imaging modalities [4, 8, 12].

The purpose of the proposed research is to evaluate the added value of  $^{68}\text{Ga}$  PSMA-11 PET/CT in relation to detect additional primary prostate cancer lesions compared to mp-MRI in a group of patients with elevated PI-RADS scores and PSA. We propose that the addition of early dynamic  $^{68}\text{Ga}$  PMSA-11 PET/CT imaging to the more usual delayed imaging will enhance detection of primary lesions and additional lesions not detected on the mp-MRI. In addition, the dynamic imaging will allow us to evaluate the kinetics of uptake in the prostate gland. It is possible that even in the absence of focal uptake, hyperemia of the gland could indicate the presence of an occult primary.

A second purpose of this research is to examine the value of  $^{68}\text{Ga}$  PSMA-11 PET/CT in this same group of patients in detecting metastatic disease at initial staging in comparison with current standard of care imaging such as CT and MRI.

**1.5 Correlative Studies**

**2.0 N/ASTUDY OBJECTIVES**

**2.1 Primary Objectives**

- 2.1.1 To assess whether  $^{68}\text{Ga}$  PSMA-11 PET/CT can detect additional primary prostate cancer lesions through use of early dynamic PET/CT imaging in comparison to mp-MRI in patients with PI-RADS v2.1 score 5 (with any PSA), or score 4 and PSA  $\geq 10$  ng/mL.

**2.2 Secondary Objectives**

- 2.2.1 To assess whether  $^{68}\text{Ga}$  PSMA-11 PET/CT can detect additional sites of metastatic disease at staging in comparison to standard of care imaging in patients with PI-RADS v2.1 score 5 (with any PSA), or score 4 and PSA  $\geq 10$  ng/mL

**2.3 Exploratory Objectives**

None

---

## 2.4 Endpoints

The primary endpoint is to determine per lesion sensitivity of  $^{68}\text{Ga}$  PSMA-11 for the detection of prostatic lesions in patients with elevated PSA and abnormal mp-MRI of the prostate (as defined as at least one lesion with PI-RADS v2.1 score 5 with any PSA or score 4 and PSA  $\geq 10$  ng/mL). A second endpoint will be to determine per person sensitivity of  $^{68}\text{Ga}$  PSMA-11 for the detection of metastatic disease, compared to standard of care imaging.

## 3.0 Subject ELIGIBILITY

Eligibility waivers are not permitted. Subjects must meet all of the inclusion and exclusion criteria to be registered to the study. Study treatment may not begin until a subject is registered.

### 3.1 Inclusion Criteria

- 3.1.1 Patients with suspected prostate cancer (e.g., abnormal digital rectal exam, elevated and/or rising PSA) as determined by referring physician
- 3.1.2 Patients must have had a diagnostic, standard of care mp-MRI of the prostate with at least one lesion with a PI-RADS v2.1 score  $\geq 4$
- 3.1.3 In men with PI-RADS v2.1 score 4, PSA should be  $\geq 10$  ng/mL. In men with at least one PI-RADS v2.1 score 5 lesion, there is no restriction on PSA level.
- 3.1.4 Patients must be scheduled for biopsy or radical prostatectomy
- 3.1.5 Patients must be older than 18 years of age
  
- 3.1.6 Patients should not have had any type of curative or palliative therapy for prostate cancer before enrolling in the study
- 3.1.7 Patients must be medically stable as judged by the patient's physician
- 3.1.8 Patients must be able to lie still for a total of 60 minutes for the PET/CT scans
- 3.1.9 Ability to understand and the willingness to sign a written informed consent

### 3.2 Exclusion Criteria

- 3.2.1 Patients who have had a prior prostatectomy or radiotherapy for prostate cancer cannot participate in the study
- 3.2.2 Patients who have had a prior biopsy for prostate cancer cannot participate in the study
- 3.2.3 Patients who have been treated for cancers other than skin cancers
- 3.2.4 Subjects may not be receiving any other investigational agents for the treatment of the cancer under study
- 3.2.5 Patients may not weigh more than the maximum weight limit for the PET/CT scanner table ( $>200\text{kg}$  or 440 lbs)

---

- 3.2.6 History of allergic reactions attributed to compounds of similar chemical or biologic composition to  $^{68}\text{Ga}$  PSMA-11 or other agents used in the study such as gadolinium-based intravenous contrast agent used during the mp-MRI
- 3.2.7 Prior TURP/BPH procedures, including steam/laser therapies.

## 4.0 TREATMENT PLAN

### 4.1 Injection of $^{68}\text{Ga}$ PSMA-11

This is a nontherapeutic imaging only study. There will be a single IV injection of 1.8 – 2.2 MBq (0.049-0.059 mCi) per kilogram of body weight of  $^{68}\text{Ga}$  PSMA-11 [15]. Injections will be performed in the PET/CT Imaging Services located on the 2nd floor of the Clements Building at UT Southwestern Medical Center.

### 4.2 Scan Acquisition

Patients will be scanned on a 128 slice PET/CT scanner. The patient will be positioned supine, with arms elevated above the head as tolerated by the patient. Data acquisition will occur as 2 discrete components: 1) a dynamic part (dPET/CT studies) and the static part (whole-body PET/CT). With the patient on the scanning table, the patient will be injected with  $^{68}\text{Ga}$  PSMA-11 and dPET/CT scanning will be performed over the pelvic area for 30 minutes [11, 12, 16]. The dPET/CT will be obtained in list mode with dynamic frames acquired at 10 x 30 seconds, 5 x 60 seconds, 5 x 120 seconds and 2 x 300 seconds. At 60 minutes post injection, a standard whole body PET scan with images from vertex of the skull to the feet will be acquired at 2-3 minutes per bed step, adjusted for body weight, along with CT images over the same range. The manufacturer's CT dose exposure limit software will be utilized. CT data will be used for attenuation correction and for anatomic localization of uptake sites [15]. The CT data will be reconstructed with soft tissue (B40f) and bone (B80) kernels.

### 4.3 Imaging Analysis

For the dynamic scan, all frames will be summed to produce a single image over the pelvis. This image will be visually evaluated for focal uptake in and around the prostate gland. In addition, the dynamic image frames will also be used to construct time activity curves comparing post injection time vs standard uptake value (SUV) of  $^{68}\text{Ga}$  PSMA-11 uptake. These curves will be constructed with volumes of interest in the prostate as a whole, in any visible focal prostate lesions and over the common left iliac artery to provide an arterial input curve. If metastatic lesions are detected on this scan, separate time activity curves will be calculated as well.

Whole body images will be visually and quantitatively evaluated independently by two experienced PET/CT readers. The readers will first assess whether the primary tumor is visually distinguishable from the surrounding prostate tissue. A prostate tumor will be judged positive if the focal tracer uptake is higher than that of the surrounding prostate tissue. For calculations of SUV, a VOI will be drawn around areas of focal uptake within the prostate using iso-contour (SUVmax). The same size VOI will be drawn in the region of the uninvolved prostate. If no focal uptake is seen in the prostate, a VOI will be drawn around the prostate.

Comparisons will be made between the interpretations provided by the two PET/CT readers and the degree of agreement will be calculated. Mean and maximum SUVs will

---

be obtained on all areas of interest. Anatomic measurements of suspicious lymph nodes will be made in the short axis.

To evaluate focal uptake in lymph nodes and distant metastatic disease, VOIs will be drawn around each lesion. SUV maximum and mean will be recorded for all lesions. In addition, VOIs will be drawn around normal uptake in the prostate and a 2 cubic centimeter VOI will be drawn in the gluteal muscle, for use as normal background [7]. A lesion will be considered positive when the uptake exceeds normal background.

Because of the small number of subjects, descriptive statistics will be used, such as percentage of times a focus of uptake in the prostate can be seen on the PET/CT and whether this focus corresponds to any detectable abnormality on review of mp-MRI of the prostate. With regard to lesions outside the prostate, comparison will be made with the results from the  $^{68}\text{Ga}$  PSMA-11 scan and possible lesions seen on conventional imaging, such as pelvic CT or MRI or bone scintigraphy.

If possible, biopsy confirmation of sites of abnormal focal  $^{68}\text{Ga}$  PSMA-11 uptake will be obtained per standard of care. If patient undergoes surgery without biopsy, findings of imaging will be correlated with whole mount pathology (WMP) of the resected gland with final pathology on the surgical specimen. For surgical patients, customized molds will be created based on MRI data to optimize co-registration of cross-sectional imaging and pathology data, as previously reported by our group [17]. If a patient undergoes radiation therapy or other ablation treatment without biopsy, post treatment conventional imaging will be performed and results will be compared for regression in size

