#### **10.3 Data Analyses**

Because of the small number of subjects, descriptive statistics will be used, such as percentage of times a focus of uptake in the prostate can be seen on the PET/CT and whether this focus corresponds to any detectable abnormality on review of mp-MRI of the prostate. To be specific, we will summarize percent of incidences when 1) PET/CT is concordant with mp-MRI, 2) uptake seen on PET/CT but normal on mp-MRI and 3) no uptake on PET/CT but abnormal seen on mp-MRI. This will be displayed in a two-by-two contingency table.

Comparison will also be made to pathologic specimens from biopsy and/or prostatectomy (as reference standard) to correlate whether abnormal foci of tracer uptake correspond to sites of tumor. The per-lesion diagnostic performance of PET/CT (sensitivity and false positives) will be reported. This will be displayed in a two-by-two contingency table.

With regard to lesions outside the prostate, comparison will be made of the results from the  $^{68}\text{Ga}$  PSMA-11 scan and possible lesions seen on conventional imaging, such as pelvic CT or MRI or bone scintigraphy. To be specific, we will summarize percent of incidences when 1) PET/CT is concordant with pelvic CT/MR/BS, 2) uptake seen on PET/CT but normal on pelvic CT/MR/BS and 3) no uptake on PET/CT but lesion seen on pelvic CT/MR/BS. This will be displayed in a two-by-two contingency table.

If possible, biopsy confirmation of sites of abnormal focal  $^{68}\text{Ga}$  PSMA-11 uptake outside the prostate gland will be obtained. If biopsy is not possible due to position or size of suspected lesion, post treatment conventional imaging will be performed and results will be compared for regression in size. The per-site diagnostic performance of PET/CT (sensitivity and false positives) will be reported. This will be displayed in a two-by-two contingency table.

Agreement between two readers in continuous measurements (mean and max SUV) will be assess by intraclass correlation coefficients (ICC) and Bland-Altman plots per area of interest. Agreement between two readers in discrete measurements (visual distinguishability of primary tumor, additional primary lesion, sites of metastasis) will be assessed by Cohen's kappa.

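### Sections 4.3 and 10.3 leave open which specimen is the per-lesion reference standard in men who have both a post-scan biopsy and a prostatectomy

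*Combined protocol and SAP*

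**What the plan says.** The primary endpoint (2.4) is per-lesion: "The primary endpoint is to determine per lesion sensitivity of" the tracer for prostatic lesions.

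Section 4.3 sets out how imaging findings are verified. Biopsy comes first: "If possible, biopsy confirmation of sites of abnormal focal" tracer uptake is to be obtained under standard of care. Next comes the surgical case: "If patient undergoes surgery without biopsy, findings of imaging will be correlated with whole mount pathology (WMP) of the resected gland". The sentence after that has no biopsy condition: "For surgical patients, customized molds will be created based on MRI data to optimize co-registration of cross-sectional imaging and pathology data". The list ends with men who have radiation or ablation without biopsy, for whom follow-up imaging is used.

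Section 9.0 has tissue from either procedure compared with the imaging. Section 10.3, which defines the analysis of per-lesion sensitivity and false positives, says: "Comparison will also be made to pathologic specimens from biopsy and/or prostatectomy (as reference standard". It does not name whole mount, and it does not rank the two specimens.

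Two eligibility rules determine who can reach each route. Inclusion 3.1.4: "Patients must be scheduled for biopsy or radical prostatectomy". Exclusion 3.2.2: "Patients who have had a prior biopsy for prostate cancer cannot participate in the study".

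**The concern.** A man can enter unbiopsied, have the scan, be biopsied and then have a prostatectomy. For him the sections point different ways. Taken at its word, 4.3 gives whole-mount correlation only to men operated on without biopsy, so he is scored on biopsy. Under 10.3 both specimens qualify, with no rule for what to do when they disagree or when one shows foci the other does not.

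The choice matters because the specimen fixes the denominator of sensitivity. Biopsy aimed at PET-positive sites cannot by itself reveal a focus that PET missed. Such a focus is counted only if a core aimed elsewhere happens to reach it. Whole-mount sections show foci that neither imaging method marked, and can confirm or refute a PET-only focus that no core reached. Section 1.1 reports that mp-MRI identified less than half of individual lesions when judged against whole mount, so uncounted foci could be numerous. The primary objective, additional lesions relative to mp-MRI, depends on the same verification. If the choice stays open, it can be made after the scans and specimens have been read, between two denominators that give different answers.

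**Working it through.** The plan has no calculated figure to reproduce: 10.2 gives up to 20 men without a sample size calculation, and the analysis is descriptive.

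**Step 1. Reference specimen by route**

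| Post-scan biopsy | Prostatectomy | 4.3 read literally | 10.3 |
|---|---|---|---|
| no | no | none | none |
| no | yes | whole mount | prostatectomy |
| yes | no | biopsy | biopsy |
| yes | yes | biopsy | biopsy and prostatectomy |

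Men with biopsy, plus men with surgery and no biopsy, are the same set as men with biopsy or surgery. So both sections have pathology on the same men. They differ only in the last row.

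**Step 2. How many men are in the last row**

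Number = N × share operated on × share of those biopsied first. N = 20 is from 10.2. Neither share is in the documents, so both are assumptions.

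- Half operated on: 20 × 0.5 = 10 men.
- Biopsied first 0%, 50%, 90% or 100%: the reference differs in 0, 5, 9 or 10 men. Literal 4.3 then gives whole mount in 10, 5, 1 or 0 men, and 10.3 gives surgical pathology in 10.
- With 25-100% operated on and 0-100% biopsied first, the range is 0 to 20 men.

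**Step 3. What the specimen does to sensitivity in these men (illustration)**

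All inputs are assumptions, except that 45% MRI-visible is chosen to agree with the statement in 1.1 of less than half.

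- 8 men with both procedures × 2.5 foci = 20 foci. MRI-visible V = 0.45 × 20 = 9; MRI-occult I = 11.
- PET detects a share pv = 0.85-0.90 of visible foci and pi = 0.30-0.40 of occult foci.
- Biopsy samples every visible focus, a share s = 0.5-1 of the PET-only foci, and a share q = 0.1-0.3 of foci negative on both.

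Whole mount: sensitivity = 0.45·pv + 0.55·pi.

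- Lowest: 0.45 × 0.85 + 0.55 × 0.30 = 0.548.
- Highest: 0.45 × 0.90 + 0.55 × 0.40 = 0.625.
- So 55-63%, on 20 foci.

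Biopsy: sensitivity = (pv·V + pi·I·s) / (V + pi·I·s + (1 − pi)·I·q).

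- Lowest (pv 0.85, pi 0.30, s 0.5, q 0.3): (7.65 + 1.65) / (9 + 1.65 + 2.31) = 9.30 / 12.96 = 0.718.
- Highest (pv 0.90, pi 0.40, s 1, q 0.1): (8.10 + 4.40) / (9 + 4.40 + 0.66) = 12.50 / 14.06 = 0.889.
- So 72-89%, on 11.4 to 15.4 foci.

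Biopsy gives the higher figure at all 16 corners of these inputs, by 14 to 30 percentage points. The percentages do not depend on the number of men, because V and I scale together. The model already lets some cores reach foci that PET missed. With cores taken only from PET-positive sites there would be no missed foci to count.

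**The case against.** The strongest reply is that 4.3 excludes nothing. It says what happens when surgery occurs without biopsy; it does not say that whole mount is ignored otherwise. In context the sentence can be read as one step in a fallback list that ensures verification where biopsy is lacking. The unconditional mold sentence, 9.0 and the *and/or* in 10.3 all point to surgical pathology in every operated man, and 10.3 is the section that defines the analysis.

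Much of this stands. A reader might infer that 4.3 is a firm rule discarding whole-mount data, but the text does not say so, and preparing molds for glands that would go unused would make little sense. What does not follow is that the matter is settled: the condition is still in 4.3, and even 10.3 does not say which specimen governs when both exist.

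Two other stronger readings fail. One is that the sections verify different men; step 1 shows that they do not. The other is that the no-prior-biopsy exclusion leaves the surgery-without-biopsy route nearly empty. The exclusion bars only biopsy before entry, and with 3.1.4 it admits an unbiopsied man scheduled directly for prostatectomy. How many take that route is a judgment about practice, for which the documents give no figure.

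It is also fair to say that this is a descriptive pilot with no hypothesis test. That limits the consequences, but the sensitivity estimate is the study's main product.

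**Conclusion.** The concern holds as an unresolved conflict over the reference specimen. The condition in 4.3 does not agree with its own next sentence, with 9.0 or with 10.3, and no rule covers men with both procedures. The number affected is unknown: 0 to 10 if 10 of 20 are operated on.

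The direction is clearer than the size. If 4.3 is followed literally, per-lesion sensitivity in these men tends to be too high, because foci missed by PET are under-counted. The contrast of 72-89% with 55-63% applies only to men with both procedures, rests on assumed detection and sampling rates, and supposes that whole mount goes unused in those men. It shows that the choice can matter; it does not predict the trial's result. The effect on the whole-study estimate would be smaller, in proportion to the share of foci that come from these men.

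This should be corrected before the per-lesion analysis is done.

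**What to change.** In 4.3, delete *without biopsy* from the surgery sentence, so that whole-mount correlation applies to any man who has a prostatectomy.

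In 10.3, add a rule: for the per-lesion analysis, the co-registered whole-mount specimen is the reference standard in every man who undergoes prostatectomy, whether or not he was biopsied first; biopsy is the reference only in men not operated on.

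The cost is two words removed and one sentence added. The change concerns which existing specimen is analysed, not who is biopsied or operated on. No procedure is added, because molds for surgical patients (4.3) and review of the tissue (9.0) are already planned. The drawback is that the reported sensitivity will probably be lower than one based on biopsy.

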## 9.0 CORRELATIVES/SPECIAL STUDIES

Standard of care imaging tests will be performed by the treating physician as detailed above.

Tissue obtained at the time of prostatectomy or biopsy will be reviewed for correlation with imaging tests.

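### Nothing keeps the pathology tumor map, or its matching to PET foci, independent of the PET result that it is used to judge

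*Combined protocol and SAP*

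**What the plan says.** Section 2.4: "The primary endpoint is to determine per lesion sensitivity of" the tracer for lesions in the prostate.

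Section 10.3 names the truth: "Comparison will also be made to pathologic specimens from biopsy and/or prostatectomy (as reference standard"). It frames the comparison as a check on PET foci, "to correlate whether abnormal foci of tracer uptake correspond to sites of tumor", and then says "The per-lesion diagnostic performance of PET/CT (sensitivity and false positives) will be reported".

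Three places describe how tissue and imaging meet:

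- Section 9.0: "Tissue obtained at the time of prostatectomy or biopsy will be reviewed for correlation with imaging tests".
- Section 4.3, for patients who have surgery without biopsy: "findings of imaging will be correlated with whole mount pathology (WMP) of the resected gland with final pathology on the surgical specimen". When a gland is removed, the same section also provides an aid to slicing it: "customized molds will be created based on MRI data to optimize co-registration of cross-sectional imaging and pathology data".
- Section 4.3, on tissue sampling: "If possible, biopsy confirmation of sites of abnormal focal" uptake is to be obtained under standard care.

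The only independence stated anywhere is between the two PET/CT readers of the whole-body images (section 4.3). Section 7.3 notes in general terms that the study has no blinding; it does not address the pathology reading. No section says who outlines tumor, in what order tissue and PET are read, when the tumor map is final, or how close a PET focus must lie to a tumor focus to count as a match.

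**The concern.** The tumor map does two jobs. The number of foci on it is the denominator of sensitivity, and their positions sort each PET focus into true or false positive. If the map, or the matching, is made with PET in view, the reference standard depends on the test it is meant to judge.

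This could happen in three ways, with different effects:

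- **Re-calling.** A closer look under a PET focus adds tumor to the map. Sensitivity rises and false positives fall.
- **Generous matching.** A PET focus is paired with a nearby tumor that it did not really detect. Sensitivity rises and false positives fall.
- **Unmapped foci.** Small tumors in PET-quiet areas are not outlined. Sensitivity rises; false positives do not change.

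All three act mainly on small or additional foci. Section 1.1 describes these as typical of what mp-MRI misses, and they are what the primary objective (section 2.1) hopes PET will find. Section 10.2 says that the results are to support a larger study, so an inflated estimate would carry forward. A map drawn with PET in view cannot be made independent afterwards.

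**Working it through.** **Text check.** Sections 2.4, 4.3, 7.3, 9.0 and 10.3 were set side by side, and the rest of the document was searched for four things: masking of the pathologist to PET, an order of reading, a lock on the tumor map before matching, and a location rule for a match. None was found. The nearest safeguard is the mold in section 4.3. It is built from MRI, not PET, and improves registration of slices to images. It does not govern what is called tumor or what counts as a match.

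**Size.** The plan has no figure to reproduce: it expects up to 20 patients, with no formal sample-size calculation and no expected lesion count or sensitivity. All counts below are therefore assumptions.

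Assumed starting point: 30 tumor foci on an independent map, 18 detected, 12 missed, 8 false-positive PET foci.

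Let r = PET foci re-called as tumor, u = PET-negative foci left off the map, and m = false-positive foci paired with a missed tumor.

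- Re-calling and omission: sensitivity = (18 + r) / (30 + r − u); false positives = 8 − r.
- Generous matching: sensitivity = (18 + m) / 30; false positives = 8 − m.

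| Change | Sensitivity | False positives |
|---|---|---|
| None | 18/30 = 60.0% | 8 |
| r = 2 | 20/32 = 62.5% | 6 |
| r = 4 | 22/34 = 64.7% | 4 |
| u = 2 | 18/28 = 64.3% | 8 |
| u = 4 | 18/26 = 69.2% | 8 |
| m = 2 | 20/30 = 66.7% | 6 |
| m = 4 | 22/30 = 73.3% | 4 |
| r = 4 and u = 4 | 22/30 = 73.3% | 4 |

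The last row needs half of the false positives to be re-called (4 of 8) and a third of the missed foci to be unmapped (4 of 12), both at once. It is an upper illustration, not an expected value.

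**Range.** With four changed calls, 30 to 50 foci and a true sensitivity of 50% to 70%, the gain is about 2 to 6 points from re-calling, 4 to 11 from unmapped foci, and 8 to 13 from generous matching.

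**Against sampling error.** The exact 95% interval for 18/30, treating foci as independent, is about 41% to 77%. Every shifted estimate in the table lies inside it.

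**The case against.** The strongest reply is that silence is not dependence. A natural reading of section 4.3 is that imaging is compared with a finished pathology report, and the wording in section 9.0 gives a purpose, not an order of reading. That stands. A reader might infer that the pathologist will read tissue with the PET result in hand. The documents do not say so, nor do they mention extra levels or directed re-review. What they support is that nothing prevents it. Since section 11.6 requires conduct as the protocol describes, an unwritten habit is not a safeguard.

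Three further inferences are tempting and do not hold:

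- That the mold makes pathology depend on the test. It is based on MRI and is a partial safeguard, for registration.
- That PET-directed biopsy is the same problem. It decides which tissue is sampled, which is a separate bias; PET-quiet areas stay unsampled however the tissue is read.
- That every error helps PET on both measures. Unmapped PET-negative foci leave false positives unchanged, and some tumor found on a closer look would be real.

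It can also be said that this is a small descriptive pilot whose interval is wider than the bias. That is true, and it limits the weight of the point. But an interval displays imprecision; it does not display a shift in one direction.

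**Conclusion.** The gap is real and bears on the primary endpoint: the plan does not keep the tumor map, or its matching to PET foci, independent of PET. Whether bias will occur cannot be told from the documents. If it does, its direction is known for each mechanism.

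On the assumed 30 foci, four changed calls by one mechanism move sensitivity from 60% to between 65% and 73%. False positives go from 8 to 4 under re-calling or generous matching and stay at 8 when foci are only left unmapped. The 73% reached by combining re-calling and omission should not be read as the expected effect, because it stacks two assumed mechanisms.

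This should be corrected before the first imaging-pathology correlation. It does not affect the sample size.

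**What to change.** State in sections 4.3, 9.0 and 10.3 that:

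1. Tumor foci on whole-mount sections are outlined, numbered and recorded by location, size and grade without PET findings, and this map is locked before the correlation.
2. PET foci are likewise recorded and locked before pathology is shown.
3. The primary two-by-two table uses the two locked maps, matched by a location rule written beforehand.
4. Foci found only on PET-directed re-review are flagged, and the table is shown a second time with them included.

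Also note in section 4.3 that the MRI-based mold aids registration but does not replace this separation.

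Clinical specimen handling, access to mp-MRI and clinical core labels need not change. The cost is a change in the order of work and a flag on the data form. If the pathologist has already seen the PET report, someone else would have to draw the study map; the documents do not say whether that will arise. The downside is that a few real foci found only on re-review leave the primary count, so a PET focus over such a tumor scores there as a false positive. The second table shows how much this matters.

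The change does not remove the bias from choosing biopsy sites by PET uptake. That should be stated as a limitation for patients whose only tissue is biopsy.
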